#### 7.5.2 DAY 2: Inpatient Follow-up – Bronchoscopy T5

For a subject assigned to lung PK timepoint group T5:

- Perform bronchoscopy with BAL on Day 2 at 24 h (± 1 h) after dosing as described for subjects in cohorts T1-T4 (see Section 7.5.1, Day 1, *After Dosing*).
  - Collect BAL samples for PK analysis once per subject at the assigned timepoint, 24 h (±1 h) (T5) after initiation of dosing, as described in Section 8.5, corresponding to the assigned cohort T5.

Note 1: Collect plasma sample for total apramycin concentration within 5 min of the corresponding BAL procedure at 24 h ( $\pm$  1 h) after initiation of the infusion. If collection of BAL samples is delayed, plasma sample will be collected at the indicated nominal timepoint (and allowable windows), and an additional plasma PK will be collected within 5 min after the last BAL sample. (See Section 8.5.1) Note 2: Urea will be measured in plasma collected at the same nominal timepoint as the plasma PK sample or in the plasma PK sample that is collected within 5 min after the last BAL sample.

- Monitor subject closely until fully recovered per bronchoscopy instructions.
  - Provide oxygenation as needed.

For all subjects:

- Obtain single 12-lead standard ECG with 10-sec rhythm strip at 24 h (±1 h) and 36 h (±1 h) after dosing.
- Obtain VS at 24 h  $(\pm 1 h)$  and 36 h  $(\pm 1 h)$  after dosing.

- Obtain blood (plasma) PK samples for total apramycin at 24 h (±1 h) and 36 h (± 1 h) after dosing.
  - An aliquot of plasma PK collected at 36 h ( $\pm$ 1 h) after starting the IMP infusion will be used in the protein binding test (for the measurement of free apramycin).
- Obtain blood and urine samples for safety clinical laboratory tests that include a calculation of GFR by the CKD-EPI equation at 24 h (±1 h) after dosing.
- Check on infusion site at 24 h ( $\pm$ 1 h) and 36 h ( $\pm$ 1 h) after dosing.
- Perform TEAE and SAE assessments.
- Perform symptom-directed (focused) PE for evaluation of TEAEs as needed.
- Document ConMeds.
- Encourage water intake at least 2 L daily Document time and volume consumed.
- Counsel to avoid rigorous physical activity and avoid caffeinated beverages.

#### 7.5.3 DAY 3: Inpatient Follow-up

- Obtain 12-lead standard ECG with 10-sec rhythm strip at 48 h (±1 h) and 60 h (±1 h) after dosing.
- Obtain VS at 48 h ( $\pm$ 1 h) and 60 h ( $\pm$ 1 h) after dosing.
- Obtain blood (plasma) PK samples for total apramycin at 48 h (±1 h) and 60 h (±1 h) after dosing.
- Obtain blood and urine samples for clinical laboratory tests that include a calculation of GFR by the CKD-EPI equation at 48 h (±1 h) after dosing.
- Obtain blood sample for Cystatin C and urine sample for KIM-1 (exploratory biomarkers of renal injury) at 48 h (±1h) after dosing.
- Perform otoacoustic assessments.
  - Ear otoscopy.
  - Audiometry (pure tone audiometry including high frequencies).
  - DPOAEs.

Note: Day -2 otoacoustic assessments may be completed on Day 3 (+2 days) if needed.

- Check on infusion site at 48 h ( $\pm 1$  h) and 60 h ( $\pm 1$  h).
- Perform TEAE and SAE assessments.
- Document ConMeds.
- Perform complete PE.
- Counsel on use of contraception (males and females), avoidance of pregnancy (women of childbearing potential), avoidance of prohibited medication, illicit drugs, alcohol, nicotine products, vigorous exercise, and exposure to loud noises.
- Instruct on the next scheduled visit.
- Discharge subject from the CTU after review of clinical laboratory tests, ECGs and other assessments by PI or authorized clinician and audiologist.

Note 1: If the time of discharge is late in the evening, due to delays in starting procedures on Day 1 or personal reasons (such as distance from residence), the subject may stay in the CTU overnight and be discharged the following morning.

Note 2: If otoacoustic assessments could not be performed on Day 3, the subject will be discharged from the CTU on Day 3 after all other assessments are completed. Otoacoustic assessments will be completed up to Day 3 (+2 days) as outpatient.

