## 7.3 Check-in (Day -2)

Subjects meeting all inclusion and no exclusion criteria at Screening Visit will check into the CTU on Day -2 and the following procedures will be performed:

- Review inclusion/exclusion criteria to confirm the subject remains eligible for admission.
- Update MH.
- Update Prior Medications.
- Obtain VS.
- Obtain body weight.
- Perform complete PE.
- Obtain blood and urine samples for clinical laboratory tests that include a calculation of GFR by the CKD-EPI equation (for determining eligibility).

- For all women, a urine β-HCG pregnancy test will be done, and negative results confirmed before dosing.
- Obtain urine sample for illicit drugs and drugs of abuse (urine drug screen) and cotinine.
- Perform alcohol breathalyzer test.
- Obtain sample for serum Cystatin-C.
- Obtain sample for urinary KIM-1.
- Obtain a single 12-lead ECG with 10-sec rhythm strip.
- Perform otoacoustic assessments.
  - Ear otoscopy.
  - Audiometry (pure tone audiometry including high frequencies).
  - DPOAEs.

Note: Day -2 otoacoustic assessments may be completed on Day -4 or Day-3 as if needed.

- Admit eligible subjects in the CTU.
- Counsel to avoid rigorous physical activity, encourage good hydration, avoid caffeinated beverages and exposure to loud noises.

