## 8.4 Ear Examination and Otoacoustic Testing

Ear exams and otoacoustic tests will be performed by licensed and experienced audiologists at the Audiology section of the ENT department of the UTMC. The following tests will be performed at the indicated study visits. These tests may be performed at the screening visit, or at a second screening visit due to time restrictions on the initial visit.

- Ear otoscopy, Valsalva test, Tympanometry and Stapedial Reflexes (Screening visit).
- Ear otoscopy only (Day -2 [or Day -4 or Day -3 if needed], Day 3 (+2 days), Day 14 (± 3 days) and Day 30 (± 4 days), or ET).
- Audiometry.
  - Pure tone audiometry at standard frequencies, 0.5 to 8 kHz (Screening visit).
  - Pure tone audiometry at standard (0.5 to 8 kHz) and higher frequencies (Day -2 [or Day -4 or Day -3 if needed], Day 3 (+2 days), Day 14 (± 3 days), and Day 30 (± 4 days), or ET.
- Distortion product otoacoustic emissions (DPOAEs) at Screening Visit, and on Day -2 [or Day -4 or Day -3 if needed], Day 3 (+2 days), Day 14 (± 3 days), and Day 30 (± 4 days), or ET.

Note 1: On Day 3, ear otoscopy, audiometry and DPOAEs can be done at any time.

Note 2: If otoacoustic assessments could not be performed on Day 3, the subject will be discharged from the CTU on Day 3 after all other assessments are completed. Otoacoustic assessments will be completed up to Day 3 (+2 days) as outpatient.

Audiology records will be obtained by the CTU staff and results will be recorded as described in the MOP.

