## 9.2 Methods and Timing for Assessing, Recording, and Analyzing Safety Parameters

#### 9.2.1 Adverse Events

#### Definitions

ICH E6 defines an AE as any untoward medical occurrence in a subject or clinical investigation subject who was administered a pharmaceutical product, regardless of its causal relationship to the product. An AE can therefore be any unfavorable and unintended sign (including an abnormal laboratory finding), symptom, or disease temporally associated with use of the product,

DMID Protocol 20-0012	Version 5.0
Apramycin	10 July 2023

and are described as treatment-emergent AEs (TEAEs). The occurrence of a TEAE may come to the attention of study personnel during study visits and interviews, or by a subject presenting for medical care.

The FDA defines an AE as any untoward medical occurrence associated with the use of a drug in humans, whether it is considered drug-related or not.

Any systemic medical condition, VS and ECG measurement, and clinical safety lab test value that is present on Day 1 prior to dosing will be considered a baseline finding for the purpose of data analysis. For ear and otoacoustic testing, baseline comprises assessments performed on Day -2. However, if the condition increases in severity or frequency after IMP administration at any time during the trial, it will be recorded as a TEAE.

Any medical condition that is reported after screening but before study drug administration will be evaluated and reported as MH update.

All TEAEs will be graded for severity according to Appendix B, Table 2, Table 3, and Table 4 and for relationship to the study drug.

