## **3.3.** Study Definitions and Derived Variables

#### **3.3.1.** Timepoints for Safety and PK Endpoints

Table 1 shows the analysis timepoints in the order that will appear in tables and figures along with the safety and PK endpoints measured at each timepoint for all participants. Endpoints analyzed by timepoint include chemistry clinical laboratory results (CHEM), hematology clinical laboratory results (HEM), coagulation clinical laboratory results (COAG), and urinalysis laboratory results (UA); urinary KIM-1 and serum cystatin C; vital signs (VS); ECG; ENT examination and otoacoustic (pure-tone audiometry and DPOAE) tests (listed in the table below as Audiology); and blood (plasma) PK and lung BAL PK results (see Section 3.3.2 for derivations of BAL PK parameters). Serology, toxicology, and pregnancy testing at Screening and/or Check-In will not be included in tables or figures but will be presented in listings.

Analysis Timepoint	Abbreviated Label	Endpoints
Screening	N/A	CHEM, HEM, COAG, UA, VS, ECG, Audiology
Check-In	D-2	CHEM, HEM, COAG, UA, KIM-1, Cystatin C, VS, ECG, Audiology
Day -1	D-1	VS, ECG
Day 1, Pre-Dose	0 h	CHEM, HEM, COAG, UA, KIM-1, Cystatin C, VS, ECG, Plasma PK
Maximum Severity Post Baseline	N/A	CHEM, HEM, COAG, UA, VS, ECG, Audiology
Day 1, 0.5 h Post-Dose	0.5 h	VS, Plasma PK, BAL PK
Day 1, 1 h Post-Dose	1 h	VS, ECG, Plasma PK
Day 1, 2 h Post-Dose	2 h	Plasma PK, BAL PK
Day 1, 4 h Post-Dose	4 h	VS, ECG, Plasma PK, BAL PK
Day 1, 8 h Post-Dose	8 h	Plasma PK, BAL PK
Day 1, 16 h Post-Dose	16 h	VS, ECG, Plasma PK
Day 2, 24 h Post-Dose	24 h	CHEM, HEM, COAG, UA, VS, ECG, Plasma PK, BAL PK
Day 2, 36 h Post-Dose	36 h	VS, ECG, Plasma PK
Day 3, 48 h Post-Dose	48 h	CHEM, HEM, COAG, UA, KIM-1, Cystatin C, VS, ECG, Plasma PK
Day 3, 60 h Post-Dose	60 h	VS, ECG, Plasma PK
Day 3 a	D3	Audiology
Day 14	D14	CHEM, HEM, COAG, UA, KIM-1, Cystatin C, VS, ECG, Audiology
Day 30	D30	KIM-1, Cystatin C, Audiology
a Day 3 refers to any time on Day 3.		

 Table 1:
 Analysis Timepoints for Safety and PK Endpoints

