#### **3.3.3.** Baseline

Baseline for clinical laboratory, VS, and audiology results will be defined as the last value recorded before administration of study drug.

For ECG measurements, pre-dose baseline is defined as the last value recorded before administration of study drug, and time-matched baseline is defined as the value recorded at the same timepoint on the day before administration of study drug (Day -1) as on Day 1. If triplicate ECG measurements were performed, the mean value of the ECG measurements will be used as the pre-dose and time-matched baseline values.

Baseline height, weight, and body mass index (BMI) will be the measurements obtained at Screening. Age will be based on age at the time of enrollment.

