- 12-lead standard ECG
  - ECG will be performed in either triplicate or single at Screening, Check-In (Day -2), Day -1 (at timepoints matching those on Day 1), Day 1 (pre-dose and 1 h, 4 h, and 16 h post-dose), Day 2 (24 h and 36 h post-dose), Day 3 (48 h and 60 h post-dose), and Day 14.
    - For ECG measurements performed in triplicate, the mean of the replicates will be used for analysis, including analyses of change from baseline.
  - At each timepoint, the overall interpretation of the ECG will be reported as Normal; Abnormal, Not Clinically Significant (NCS); or Abnormal, Clinically Significant (CS). For post-dose timepoints, the change from baseline will be also reported as No change from baseline; NCS, change from baseline; or CS, change from baseline.
  - The following parameters will be measured: PR interval, QRS interval, QT interval, corrected QT interval using Fridericia's Formula (QTcF correction), RR internal, and ventricular rate.
    - For replicate ECGs recorded on Day -1 and Day 1, the mean time-matched change-frombaseline QTcF values (ΔΔQTcF) will be evaluated to quantify the QTcF prolongation. For single ECG recoded after dosing, the mean pre-dose change-from-baseline (ΔQTcF) will also be analyzed.
- Audiology
  - The following audiology tests will be conducted:
    - Valsalva test, Tympanometry and Stapedial Reflexes at Screening only.
    - Ear otoscopy at Screening, Check-In (Day -2), Day 3, Day 14, and Day 30.

- Pure tone audiometry at standard frequencies (0.5 to 8.0 kHz) at Screening and at both standard and higher frequencies (9.0 to 20.0 kHz) at Check-In (Day -2), Day 3, Day 14, and Day 30.
- DPOAEs (1.5 to 6.0 kHz) at Screening, Check-In (Day -2), Day 3, Day 14, and Day 30.
- Physical Examination
  - A complete PE to assess general appearance; head, eyes, ears, nose, and throat (HEENT); heart, lungs, abdomen, skin, musculoskeletal system, and lymph nodes; and a neurological exam will be performed at Screening, Check-In (Day -2), Day 3 (60 h post-dose), and Day 14.
  - An abbreviated PE will be performed at Day -1. An abbreviated PE differs from a complete PE in that the abdomen and neurological system are not evaluated.
  - A symptom-directed (focused) PE may be performed on Day 1 and at any time after dosing for evaluation of TEAEs.
  - Height and weight will be measured, and BMI calculated, at Screening only. Weight only will be measured on Day -2 and Day 14.

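### Protocol 7.5.3 contains a note, probably a slip, that places the Day -2 hearing tests after dosing; followed literally, it leaves a subject with no pre-dose high-frequency audiometry

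*Protocol*

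**What the plan says.** Protocol 7.5.3, directly under the Day 3 list of otoscopy, audiometry and DPOAEs, carries this note: "Note: Day -2 otoacoustic assessments may be completed on Day 3 (+2 days) if needed".

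Four other statements bear on it.

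- **What the baseline is.** Protocol 9.2.1: "For ear and otoacoustic testing, baseline comprises assessments performed on Day -2". The SAP rule (3.3.3) is worded differently: "Baseline for clinical laboratory, VS, and audiology results will be defined as the last value recorded before administration of study drug". Protocol 11.4.7 gives the same last-value-before-drug rule for audiology.
- **How far the Day -2 tests may move.** Protocol 7.3: "Day -2 otoacoustic assessments may be completed on Day -4 or Day-3 as if needed". Section 8.4 and Appendix A footnote 14 give the same two earlier days.
- **What Screening measures.** Protocol 8.4: "Pure tone audiometry at standard frequencies, 0.5 to 8 kHz (Screening visit". High frequencies start at check-in. SAP 4.5.1 has "both standard and higher frequencies (9.0 to 20.0 kHz) at Check-In (Day -2), Day 3, Day 14, and Day 30".
- **Where the +2 days belong elsewhere.** Note 2 of 7.5.3, Section 8.4, Section 9.1 and Appendix A footnote 14 all attach the window to the Day 3 tests. The SAP does not mention the window. Footnote a of its Table 1 reads "Day 3 refers to any time on Day 3".

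**The concern.** Assessing change in otoacoustic testing is a stated secondary objective, and the drug is an aminoglycoside, a class with known ototoxic risk. Change from baseline needs a pre-dose value. The note is an instruction to site staff and, as written, permits the only scheduled pre-dose high-frequency test to be done after the dose.

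The Day -1 list (7.4) and the Day 1 pre-dose list (7.5.1) contain no audiology step, and neither asks specifically whether the Day -2 hearing tests were done. A deferred test might therefore go unnoticed until after infusion. A pre-dose audiogram cannot be obtained afterwards.

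**Working it through.** The plan states no figure to reproduce. The check is a comparison of passages, with day and frequency counts.

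**1. Days.** Dosing is on Day 1 and there is no Day 0 (SAP 3.3.4).

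- Day 3 (+2 days) runs from Day 3 to Day 5, which is 3 − 1 = 2 to 5 − 1 = 4 days after dosing.
- Day -4 to Day -2 is 4 to 2 days before dosing.

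**2. The statements side by side.**

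| Place | When the Day -2 tests may be done | Which tests get +2 days |
|---|---|---|
| Protocol 7.3 | Day -4, -3 or -2 | not mentioned |
| Protocol 8.4 | Day -4, -3 or -2 | Day 3 tests |
| Protocol 9.1 | not mentioned | Day 3 tests |
| Appendix A, footnote 14 | Day -4, -3 or -2 | Day 3 tests |
| Protocol 7.5.3, Note 2 | not mentioned | Day 3 tests |
| Protocol 7.5.3, disputed note | Day 3 to Day 5 | Day -2 tests |

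Only the disputed note places the Day -2 tests after dosing.

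**3. Frequencies** (SAP 9.9 and Table 73).

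- Standard: 0.5, 1, 2, 4, 6, 8 kHz = 6.
- High: 9, 10, 11, 12.5, 14.5, 16, 18, 20 kHz = 8.
- Total per ear: 6 + 8 = 14. Screening covers the first 6 only.

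**4. A subject whose Day -2 tests are deferred under the note.**

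- *9 to 20 kHz:* Screening gives no value and the Day -2 test has moved, so there are 0 pre-dose values. Nothing is imputed (SAP 6.5), and Protocol 11.4.7 excludes subjects whose change is undefined. The loss is 8/14 = 57% of frequencies per ear. Over two ears and the three scheduled post-dose visits (Days 3, 14, 30), it is 8 × 2 × 3 = 48 of 14 × 2 × 3 = 84 scheduled change values. These are the high-frequency rows of SAP Tables 73 and 74 and that subject's contribution to Figures 101 and 102.
- *0.5 to 8 kHz and DPOAEs:* both are measured at Screening, so under the SAP rule the baseline becomes the Screening value. The Screening window is Day -28 to Day -3, so that value may be up to 28 days old at dosing instead of 2 to 4. This does not meet the Day -2 definition in Protocol 9.2.1.
- *Hearing grades:* Appendix B, Table 2 uses an audiogram from 1 to 8 kHz, inside the Screening range. The audiometry halting rule in 9.5.1 uses those grades, so it keeps a pre-dose reference.
- *DPOAE halting rule:* it refers to frequencies at which responses had been obtained before and does not name Day -2. The Screening DPOAEs supply that reference.

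**5. Share of the trial.** With 20 planned subjects, each affected subject is 1/20 = 5% of the planned high-frequency change data.

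**The case against.** The strongest reply is that this is a slip, with Day -2 written for Day 3. The note sits under the Day 3 tests, and Note 2 of the same section gives those tests the identical window. Site staff working on Day -2 follow 7.3, which is clear and lists the tests. For harm to occur, a site would have to skip them and act on one anomalous sentence filed under a post-dose visit. That is probably right. It makes the note an inconsistency and not a design choice, and it lowers the likelihood of harm. It does not change what the sentence permits.

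A reader might infer more than the documents support in three respects.

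- **A post-dose value could serve as baseline and subtract an early drug effect.** Protocol 11.4.7 and SAP 3.3.3 both fix the audiology baseline as the last value before study drug. A Day 3 to Day 5 test cannot be the analysis baseline, so the consequence is missing data and not that bias.
- **Grading and the ototoxicity halting criteria would be disabled.** They would rest on an older test, but both keep a Screening reference.
- **A permitted Day 4 or Day 5 test has no analysis timepoint because SAP 9.9 keeps unscheduled tests out of tables and figures, apart from maximum severity.** A Day 3 test done inside its protocol window is a scheduled test. SAP Table 1 also omits the Day 14 and Day 30 windows, and nobody would say those visits lack a timepoint. The SAP is Version 1.0 of 7 February 2023 and cites protocol v3.0, whereas the protocol is v5.0 of 10 July 2023. A clarifying footnote would help, but no loss of data is shown.

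**Conclusion.** The note in 7.5.3 is wrong as written. It contradicts 7.3, 8.4, 9.2.1 and Appendix A footnote 14, and it sits awkwardly with Note 2 of its own section. The consequence is narrow: for any subject handled under it, all high-frequency change from baseline is lost (8 of 14 frequencies per ear), and the remaining hearing tests are compared with Screening instead of Day -2. The primary PK objective is unaffected.

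This rests on two assumptions: that a site would act on the note, for which the documents give no likelihood, and that no unscheduled high-frequency test was done before dosing. The loss per affected subject follows directly from the schedule and the baseline rule. The number of affected subjects may well be zero.

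**What to change.** Reconcile the note in Protocol 7.5.3 with 7.3, 8.4, 9.2.1, Appendix A footnote 14 and Note 2 of 7.5.3, so that the +2-day window applies to the Day 3 tests and the baseline otoacoustic tests are recorded before dosing. Replacing the day label in the note would do this.

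Optionally, state in footnote a of SAP Table 1 that Day 3 audiology includes the protocol's +2-day window. SAP Section 15 allows an addendum before final data lock.

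The cost is about one word in the protocol, to be carried in an amendment or clarification, and one SAP footnote. No visit, test or analysis is added.

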## 7.6 Outpatient Follow-up Period (Days 14 and 30)

Subjects will return to the CTU to have the following assessments:

#### 7.6.1 DAY 14 (± 3 days)

- Obtain 12-lead standard ECG with 10-sec rhythm strip.
- Obtain VS.
- Obtain blood and urine samples for clinical laboratory tests that include a calculation of GFR by the CKD-EPI equation.
- Obtain blood sample for Cystatin C and urine sample for KIM-1 (exploratory biomarkers of renal injury).
- Perform otoacoustic assessments.
  - Ear otoscopy.
  - Audiometry (pure tone audiometry including high frequencies).
  - DPOAEs.
- Check on infusion site.
- Perform TEAE and SAE assessments.
- Document ConMeds.
- Perform a complete PE.
- Counsel on use of contraception (males and females), avoidance of pregnancy (women of childbearing potential), avoidance of sperm donation, avoidance of prohibited medication, illicit drugs, alcohol, nicotine products, vigorous exercise, and exposure to loud noises.
- Instruct on the next scheduled visit.

#### 7.6.2 Day 30 (± 4 days) – FINAL VISIT

- Perform TEAE and SAE assessments.
- Document ConMeds.
- Obtain blood sample for Cystatin C and urine sample for KIM-1 (exploratory biomarkers of renal injury).
- Perform symptom-directed (focused PE) for evaluation of TEAEs as needed.

- Perform otoacoustic assessments.
  - Ear otoscopy.
  - Audiometry (pure tone audiometry including high frequencies).
  - DPOAEs.
- Discharge subject from the study.
- Follow up on-going TEAEs including otoacoustic abnormalities according to PI instruction to resolution or until stable.

#### 7.7 Early Termination (if needed)

- Obtain VS.
- Obtain weight.
- Check infusion site.
- Perform complete PE.
- Perform TEAE and SAE assessments.
- Update ConMeds.
- Obtain single 12-lead standard ECG with 10-sec rhythm strip.
- Obtain blood and urine for clinical laboratory tests that include a calculation of Glomerular Filtration Rate (GFR) by the CKD-EPI equation.
- Obtain blood sample for Cystatin C and urine sample for KIM-1 (exploratory biomarkers of renal injury).
- Obtain blood PK sample for total apramycin if ET occurs within 24 h of dosing.
- Perform otoacoustic assessments (ear otoscopy, audiometry [pure tone audiometry including high frequencies], and DPOAEs).
- Counsel on use of contraception (males and females), avoidance of pregnancy (women of childbearing potential), avoidance of sperm donation.

#### 7.8 Unscheduled Visit (if needed)

A subject may return to the clinic for an unscheduled visit at any time after discharge on Day 3. The following activities at a minimum will be performed:

- Perform TEAE and SAE assessments.
- Update ConMeds.
- Obtain VS.
- Perform symptom-directed (focused) PE, if applicable.
- Obtain blood and/or urine for clinical safety laboratory tests that include a calculation of GFR by the CKD-EPI equation, if applicable.

- Obtain single 12-lead standard ECG with 10-sec rhythm strip as needed for the evaluation of a TEAE, if applicable.
- Perform otoacoustic assessments, if applicable (Ear otoscopy, Audiometry [pure tone audiometry including high frequencies], and DPOAEs).

